4.3.1.1 Grade ≥ 3 non hematological toxicity

Grade ≥ 3 non-hematological toxicity felt to be related to study medication will be considered dose-limiting with the following clarifications:

- Diarrhea Grade 3 will only be considered dose limiting if it is refractory to treatment as outlined in the supportive care guidelines (section 4.4.3)
- Bloody or grade 4 diarrhea will be considered dose limiting
- Nausea or vomiting grade 3 will only be considered dose limiting if it is refractory to anti-emetic therapy and unable to be corrected to \leq Grade 1 within 24 hours
- Rise in serum creatinine to grade 3, not corrected to \leq grade 1 within 24hrs with IV fluids will be considered dose limiting
- Grade 3 metabolic toxicities unable to be corrected \leq grade 2 within 24 hours (like glucose changes, hypokalemia, hypomagnesaemia, hypophosphatemia, and hyponatraemia) will be considered dose limiting, unless patient had metabolic abnormalities at baseline. Grade 4 metabolic toxicities that are symptomatic will be considered dose-limiting regardless of duration or ability to correct.
- Other Grade 3 lab abnormalities will only be considered a DLT if they do not resolve within 2 weeks.
- Elevated bilirubin will not be considered a DLT unless >3.5 mg/dL

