4.3.1 Definitions

DLT is defined as a significant adverse events (detailed below) occurring during the DLT period (first 28 days of nivolumab treatment) that is related to nivolumab. DLT will be evaluated according to CTCAE v 4.03 criteria. Delay in starting nivolumab therapy more than 2 weeks due to toxicity regardless of attribution or grade, is considered a DLT

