4.4 Toxicity Management: Dose Delays and Discontinuation

Dosing with Yttrium-90 will follow standard of care procedures, and there will be no dose modifications.

Any patient who receives at least one dose of nivolumab will be evaluable for toxicity endpoints. Each patient will be assessed for the development of toxicity by laboratory results and physical exam at each study visit, according to CTCAE 4.03.

Nivolumab may be delayed or discontinued following the instructions detailed in section 4.4.1.

In addition, nivolumab should be discontinued for toxicities as outlined in section 4.4.2.

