 - Any Grade 3 drug-related thrombocytopenia > 7 days or associated with bleeding requires discontinuation
- Any drug-related liver function test (LFT) abnormality that meets the following criteria require discontinuation:
 - AST or ALT > 5-10 x ULN for > 2 weeks
 - AST or ALT > 10 xULN
 - Total bilirubin > 5 x ULN
 - Concurrent AST or ALT > 3 xULN and total bilirubin > 2 x ULN
- Any Grade 4 drug-related adverse event or laboratory abnormality, except for the following events which do not require discontinuation:
 - Grade 4 neutropenia ≤7 days
 - Grade 4 lymphopenia or leukopenia
 - Isolated Grade 4 amylase or lipase abnormalities that are not associated with symptoms or clinical manifestations of pancreatitis. The PI and DSMC should be consulted for Grade 4 amylase or lipase abnormalities.
 - Isolated Grade 4 electrolyte imbalances/abnormalities that are not associated with clinical sequelae and are corrected with supplementation/appropriate management within 72 hours of their onset
 - Grade 4 drug-related endocrinopathy adverse events, such as adrenal insufficiency, ACTH deficiency, hyper- or hypothyroidism, or glucose intolerance, which resolve or are adequately controlled with physiologic hormone replacement (corticosteroids, thyroid hormones) or glucose-controlling agents, respectively, may not require discontinuation.
- Any event that leads to interruption in dosing lasting > 6 weeks from the previous dose requires discontinuation, with the following exceptions:
 - Dosing interruptions to allow for prolonged steroid tapers to manage drug-related adverse events are allowed. Prior to re-initiating treatment in a subject with a dosing interruptions lasting > 6 weeks from the previous dose, the PI and DSMC must be consulted. Tumor assessments should continue as per protocol even if dosing is interrupted. Periodic study visits to assess safety and laboratory studies should also continue every 6 weeks or more frequently if clinically indicated during such dosing interruptions.

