5.0 STUDY PROCEDURES

	Screening ¹	On Treatment (1 cycle = 28 days)				Off Treatment		
Time Period	Baseline	Induction Treatment ⁹	Cycle 1 ¹⁰ (± 3 days)		Cycle 2+ (± 3 days)		End of Treatment ¹³	Follow-up ¹⁴
			D1	D15	D1	D15		
Assessment or Activity								
Informed Consent	X							
Medical history	X							
Physical exam ²	X		X		X			
ECOG status	X		X		X			
Adverse Events & ConMeds	X	X	X		X		X	X
Tumor Measurement ³	X		X ³		X ³			
Coagulation studies (INR, PT, PTT) ⁴	X ⁴							
Child-Pugh Class	X		X					
CBC with diff ⁵	X ⁵		X	X	X	X	X	
Chemistry panel ⁶	X ⁶		X	X	X	X	X	
AFP	X		X		X			
TSH with reflex T3, T4			X		X			
Hepatitis Panel ⁷	X						X	
Urinalysis	X						X	
Pregnancy Test ⁸	X	X	X				X	
ECG	X							
Angiogram ⁹	X							
Y-90 ⁹		X						
Nivolumab ¹⁰			X	X	X	X		
Correlative studies ¹¹	X		X		X ¹¹			
Archival tissue collection ¹²	X							
Survival status ¹⁴								X

1 All screening procedures should take place within 28 days of registration unless noted otherwise.

2 Includes vital signs (pulse, respirations, blood pressure), height (baseline only) and weight.

- 3 Imaging will be performed at screening, 21-28 days after Y-90 administration (during Cycle 1), and every 2 cycles (starting with Cycle 3 Day 1, ± 7 days) for the first 13 months. Imaging will then occur every 3 cycles (± 7 days) until disease progression or treatment discontinuation. Imaging will include either CT of Chest/Abdomen/Pelvis or MRI as indicated. Contrast should be used to the greatest extent possible (see section 6.1 for details).
- 4 Coagulation studies will be performed at the time of the screening angiogram. Patients who are on Coumadin will require their INR to be checked every cycle or according to the treating oncologist. If patient is on low molecular weight heparin, an Anti-Xa level should be tested to ensure it is within therapeutic range
- 5 CBC with differential will include WBC, ANC, ALC, Platelets, and Hemoglobin. CBC should be collected within 14 days prior to registration and reviewed prior to each nivolumab treatment.
- 6 Chemistry panel will be drawn at screening (within 14 days prior to registration) and pre-dose at all treatment visits. Chemistry panel will include glucose, calcium, albumin, ALT, AST, sodium, potassium, total bilirubin, alk phos, and creatinine.

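### Low magnesium and low phosphate are named as dose-limiting in 4.3.1.1, but neither is on the scheduled chemistry panel, so these DLTs are not systematically ascertained

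*Combined protocol and SAP*

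**What the plan says.** **DLT definition.** Section 4.3.1 limits DLTs to significant events "occurring during the DLT period (first 28 days of nivolumab treatment) that is related to nivolumab". Within that, 4.3.1.1 counts Grade 3 metabolic toxicities that cannot be brought to Grade 2 or below within 24 hours. The examples and the exemption read "like glucose changes, hypokalemia, hypomagnesaemia, hypophosphatemia, and hyponatraemia) will be considered dose limiting, unless patient had metabolic abnormalities at baseline". The same bullet adds: "Grade 4 metabolic toxicities that are symptomatic will be considered dose-limiting regardless of duration or ability to correct".

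**What is measured.** Section 5.0, note 6 says "Chemistry panel will include glucose, calcium, albumin, ALT, AST, sodium, potassium, total bilirubin, alk phos, and creatinine". On timing it says "Chemistry panel will be drawn at screening (within 14 days prior to registration) and pre-dose at all treatment visits", which in Cycle 1 means Day 1 and Day 15. No other row of the schedule contains magnesium or phosphate. The electrolyte eligibility criterion in 3.1.9 covers potassium, sodium and calcium only.

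**How the DLT count is used.** Section 2.1.1 defines the MTD as the highest dose with DLTs in fewer than 2 of 6 patients, and 4.3 requires six patients at whichever level is declared the MTD. There are two levels, 80 mg and 240 mg.

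**A related mismatch.** Among the events in 4.4.3 that do not require a patient to stop nivolumab is "Isolated Grade 4 amylase or lipase abnormalities that are not associated with symptoms or clinical manifestations of pancreatitis". Amylase and lipase are not on the panel either.

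**The concern.** The MTD is the Phase I primary objective, and it is decided by counting DLTs in very small groups. The Grade 3 metabolic criterion does not require symptoms, so it includes events that only a blood test would show. A site that follows the schedule exactly obtains no magnesium or phosphate result at baseline or in the 28-day window.

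Two things follow. Whether such an event is found depends on who happens to order the test, so ascertainment can differ between patients in the same cohort. And if a low value is found ad hoc in Cycle 1, the DSMC, which confirms the presence or absence of DLTs, has no baseline value to show whether that abnormality was already present.

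The error has one direction. A missed DLT lowers the count and makes it easier for a level to pass. The level that passes is carried forward: its six patients count toward the 29 in Phase Ib, and 23 more are to be treated at it.

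**Working it through.** **Step 1. Compare the DLT examples with the panel.**

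| Example in 4.3.1.1 | On the Section 5.0 panel? |
|---|---|
| Glucose | Yes |
| Potassium | Yes |
| Magnesium | No |
| Phosphate | No |
| Sodium | Yes |

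Three of the five have a scheduled input and two do not. The alkaline phosphatase on the panel is an enzyme, not phosphate.

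**Step 2. Acceptance probability.** The plan states no operating characteristics for its 3+3 rule, so there is no figure to reproduce. Let *p* be the probability that a patient has a recorded DLT. A level can be declared the MTD with 0 or 1 DLT in 6, by either of two routes:

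- 0 of 3, then 0 or 1 of the next 3: (1−p)³ × [(1−p)³ + 3p(1−p)²]
- 1 of 3, then 0 of the next 3: 3p(1−p)² × (1−p)³

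The sum is A(p) = (1−p)⁶ + 6p(1−p)⁵, which is P(Bin(6, p) ≤ 1).

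**Step 3. Effect of missed DLTs.** Let *m* be the probability that a patient's only DLT is an unmeasured magnesium or phosphate event. The level is then judged at p − m instead of p. The documents give neither p nor m, so both are assumptions. For a true rate of 0.30:

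- m = 0: 0.70⁶ + 6(0.30)(0.70⁵) = 0.1176 + 0.3025 = 0.420
- m = 0.01: 0.71⁶ + 6(0.29)(0.71⁵) = 0.1281 + 0.3139 = 0.442
- m = 0.05: 0.75⁶ + 6(0.25)(0.75⁵) = 0.1780 + 0.3560 = 0.534
- m = 0.10: 0.80⁶ + 6(0.20)(0.80⁵) = 0.2621 + 0.3932 = 0.655

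The same formula over a range of true rates:

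| True DLT rate | m = 0 | m = 0.01 | m = 0.05 | m = 0.10 |
|---|---|---|---|---|
| 0.17 | 0.729 | 0.753 | 0.844 | 0.939 |
| 0.25 | 0.534 | 0.558 | 0.655 | 0.776 |
| 0.30 | 0.420 | 0.442 | 0.534 | 0.655 |
| 0.33 | 0.358 | 0.378 | 0.464 | 0.582 |
| 0.40 | 0.233 | 0.249 | 0.319 | 0.420 |

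Acceptance rises by about 2 percentage points if m is 1%, by 9 to 12 points if it is 5%, and by 19 to 24 points if it is 10%. At m = 0 nothing changes.

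**Step 4. How plausible are the larger values?** At a true rate of 30%, m of 5 to 10 points means that these two abnormalities supply one-sixth to one-third of all DLTs. The nivolumab side-effect list in 8.2.10 and the TheraSphere table in Appendix 1 mention neither low magnesium nor low phosphate. The documents therefore give no support for values that large, and they do not rule out small ones.

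**The case against.** **These events can still be found.** Section 4.4 says "Each patient will be assessed for the development of toxicity by laboratory results and physical exam at each study visit, according to CTCAE 4.03", symptomatic Grade 4 metabolic toxicity is a DLT in its own right, and nothing bars unscheduled tests. This stands against any claim that such DLTs cannot be detected. It does not supply a test for an asymptomatic Grade 3 event. The 24-hour clause does presuppose an unscheduled repeat, but a repeat follows an abnormal first value, and for these two analytes no first value is scheduled. Section 7.2.9 requires laboratory abnormalities to be recorded; it does not order any test.

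**The list is illustrative and the exemption is general.** The five abnormalities are given as examples, and the exemption does not say that the baseline abnormality must be in the same analyte. Baseline glucose, sodium, potassium and calcium could therefore inform it in part. That is fair, but baseline magnesium and phosphate remain unknown on either reading.

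**Bias is not shown.** A reader might infer that the MTD is biased upward. The documents support the direction only if such DLTs occur. They must also be related to nivolumab, and neither safety list mentions them. With two levels, the error could arise only as accepting a level that should have failed.

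**Amylase and lipase are a separate matter.** A reader might add the 4.4.3 exception as a further set of unmeasured DLTs, or as an unworkable stopping rule. It is neither. It governs whether an individual patient stops nivolumab, and the study stopping rule in 4.9 concerns Grade 4 hyperbilirubinemia or a treatment-related death. These enzymes could reach the DLT definition only through the general clause "Other Grade 3 lab abnormalities will only be considered a DLT if they do not resolve within 2 weeks". An unmeasured, isolated, asymptomatic Grade 4 elevation leaves the patient on treatment, as the exception already allows; what is lost is the PI and DSMC consultation.

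**Leftover wording.** The amendment summary in Appendix 5 records that screening requirements for lipase, amylase and magnesium were removed because the panel did not include them. That is history, not an error, and may explain the mismatch. It does not settle it in the current text.

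**Conclusion.** The point holds as an internal inconsistency. Two abnormalities named in the DLT definition have no scheduled measurement, at baseline or on treatment, even when the plan is followed exactly. DLTs of these two kinds are not systematically ascertained, and the baseline exemption cannot be applied to these two analytes from scheduled data.

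Any effect on the MTD decision can only favour acceptance of a level, but its size is unknown. The 44%, 53% and 66% set against 42% show sensitivity at an assumed true rate of 30%; they are not estimates. If no such DLTs occur, there is no effect.

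This deserves correction because it touches the Phase I primary endpoint and is cheap to resolve. It does not show that the declared MTD is wrong. The amylase and lipase reference is a secondary point for the same reconciliation.

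**What to change.** Reconcile 4.3.1.1 with Section 5.0, note 6, in one of two ways:

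- Schedule every laboratory abnormality named in the DLT definition at baseline and within the 28-day DLT window, for example by running magnesium and phosphate on chemistry samples already drawn.
- Have the DLT text name only what the schedule measures.

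The choice is for the sponsor and investigator. In either case, state whether the baseline exemption refers to the same analyte or to any metabolic abnormality. In the same pass, check the amylase and lipase wording in 4.4.3 against the panel.

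The first route costs a small laboratory charge per sample, with no new visit or blood draw. The second costs wording only. Both need a short amendment. If Phase I patients have already been assessed, report for each of them whether magnesium and phosphate were measured in the DLT window, so that readers can see how complete the DLT count is.

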2.0 OBJECTIVES & ENDPOINTS

2.1 Primary Objectives & Endpoints

- 2.1.1 Phase I:** To identify maximum tolerated dose (MTD) of nivolumab for combination treatment of nivolumab and Y-90 in patients with advanced hepatocellular carcinoma. The MTD will be defined as the highest dose that causes dose limiting toxicities (DLTs) in <2 of 6 patients.
- 2.1.2 Phase Ib:** To evaluate the proportion of patients with objective response rate (ORR, according to RECIST criteria version 1.1) to the combination treatment of nivolumab with Y-90.

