4.3 Phase I Dose Escalation Scheme

In this phase 1/1b pilot study, the dose escalation component will be for nivolumab, starting at a dose of 80mg. Please see the table in statistical section for dose adjustments.

Phase I Dose Escalation Plan based on 3+3 design:

Dose Level	Nivolumab
1	80mg IV every 2 weeks
2	240mg IV every 2 weeks

NU Study Number: NU 16101
BMS Study Number: CA 209-615

A standard “3+3” dose escalation design will be utilized. Initially, 3 patients will be enrolled at the starting dose (level 1), after which enrollment will be temporarily suspended until all 3 patients complete the DLT evaluation period (defined as cycle 1 or the first 28 days of treatment). Once all 3 patients complete the DLT period and toxicity data has been submitted, the Data and Safety Monitoring Committee (DSMC) will review the data and confirm the presence or absence of any DLTs (defined below). The following rules will be used at each dose level to determine whether or not to proceed to the next dose level:

- If 0 of 3 patients at a given dose level experience a DLT (defined below), then escalation will proceed to the next dose level.
- If 2 or 3 of 3 patients at a given dose level experience a DLT, then one of the following must occur:
 - If this happens at level 1, the PI will discuss with DSMC and BMS to determine the necessary outcome.
 - If this happens at level 2 or beyond, the previous level will be declared the maximum tolerated dose (MTD).
- If 1 of 3 patients at a given dose level experiences a DLT, then an additional 3 slots will be added (for a total of 6 patients at that level):
 - If 1 of 6 total experiences a DLT, then escalation will proceed to the next level.
 - If ≥ 2 of 6 total experience a DLT, the previous level will be declared the MTD.

NOTE: Whichever dose level is declared the MTD must have 6 total patients treated at that level. For example, if 3 patients are treated at level 2 and 0 patients experience DLT, escalation would then proceed to level 3. However, if ≥ 2 patients at level 3 experience DLT, enrollment to level 2 would need to be re-opened to enroll an additional 3 patients at that level (with 0 or 1 DLT observed in 6 total patients) in order to declare level 2 the MTD.

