4.4.1 Dosing delays

There will be no dose modifications allowed for management of toxicities.

Patients will be allowed to delay nivolumab treatment by up to 6 weeks.

Nivolumab administration should be delayed for the following until resolution to \leq Grade 1 or baseline:

- Any Grade ≥ 2 non-skin, drug-related adverse event, with the following exceptions:
 - Grade 2 drug-related fatigue or laboratory abnormalities do not require a treatment delay
- Any Grade 3 skin, drug-related adverse event
- Any Grade 3 drug-related laboratory abnormality, with the following exceptions for lymphopenia, leukopenia, AST, ALT, or total bilirubin:
 - Grade 3 lymphopenia or leukopenia does not require dose delay
 - If a subject has a baseline AST, ALT or total bilirubin that is within normal limits, delay dosing for drug-related Grade ≥ 2 toxicity
 - If a subject has baseline AST, ALT, or total bilirubin within the Grade 1 or 2 toxicity range, delay dosing for drug-related Grade ≥ 3 toxicity
 - During Cycle 1, a delay in dosing is not required for Grade 3 total bilirubin ≤ 3.5 mg/dL

NOTE: If bilirubin worsens after the first dose of nivolumab, a delay in dosing may be warranted per physician discretion.

- Any adverse event, laboratory abnormality, or intercurrent illness which, in the judgment of the investigator, warrants delaying the dose of study medication.

Immuno-oncology (I-O) agents are associated with AEs that can differ in severity and duration than AEs caused by other therapeutic classes. Nivolumab is considered an immuno-oncology agent in this protocol. Early recognition and management of AEs associated with immune-oncology agents may mitigate severe toxicity. Management Algorithms have been developed to assist investigators in assessing and managing the following groups of AEs:

- Gastrointestinal
- Renal
- Pulmonary
- Hepatic
- Endocrinopathy
- Skin
- Neurological

The above algorithms are found in the nivolumab Investigator Brochure and appendix 3 of this protocol.

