7.2 Definitions & Descriptions

7.2.1 Adverse Event

An **adverse event** (AE) is any symptom, sign, illness or experience that develops or worsens in severity during the course of the study. Intercurrent illnesses or injuries should be regarded as adverse events. Abnormal results of diagnostic procedures are considered to be adverse events if the abnormality:

- results in study withdrawal
- is associated with a serious adverse event
- is associated with clinical signs or symptoms
- leads to additional treatment or to further diagnostic tests
- is considered by the investigator to be of clinical significance

Recording of AEs should be done in a concise manner using standard, acceptable medical terms. In general, AEs are not procedures or measurements, but should reflect the reason for the procedure or the diagnosis based on the abnormal measurement. Preexisting conditions that worsen in severity or frequency during the study should also be recorded (a preexisting condition that does not worsen is not an AE). Further, a procedure or surgery is not an AE; rather, the event leading to the procedure or surgery is considered an AE.

If a specific medical diagnosis has been made, that diagnosis or syndrome should be recorded as the AE whenever possible. However, a complete description of the signs, symptoms and investigations which led to the diagnosis should be provided. For example, if clinically significant elevations of liver function tests are known to be secondary to hepatitis, "hepatitis" and not "elevated liver function tests" should be recorded. If the cause is not known, the abnormal test or finding should be recorded as an AE, using appropriate medical terminology (e/g/ thrombocytopenia, peripheral edema, QT prolongation).

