8.2.10 Side effects

Below are safety data from 268 subjects with unresectable or metastatic melanoma and 117 patients with metastatic squamous NSCLC who received nivolumab alone. Related side effects reported in subjects receiving nivolumab alone were:

Very Frequent – Expected to occur in more than 20% of people (more than 20 out of 100 people): Fatigue (50%), Dyspnea (38%), Musculoskeletal pain (36%), Rash (21%), Increased AST (28%), Increase alkaline phosphatase (22%), Hyponatremia (25-38%)

Frequent - Expected to occur in 10% to 20% of people (10 to 20 out of 100 people): Pruritus (19%), Cough (17%), URI (11%), Peripheral edema (10%), Increased ALT (16%), Hyperkalemia (15%)

NU Study Number: NU 16101
BMS Study Number: CA 209-615

Not Frequent – Expected to occur in less than 10% of people (less than 10 out of 100 people): ventricular arrhythmia, iridocyclitis, infusion-related reactions, increased amylase, increased lipase, dizziness, peripheral and sensory neuropathy, exfoliative dermatitis, erythema multiforme, vitiligo, psoriasis

Deaths thought to be related to nivolumab when given alone were reported in approximately 0.5% of subjects treated (approximately 1 out 200 people).

For the most recent safety update, please refer to the current Investigator’s Brochure or Study Agent Prescribing Information.

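### The baseline exemption for persistent Grade 3 metabolic toxicity is not tied to the disturbance that was abnormal at baseline, so an unrelated entry abnormality can remove an event from the DLT count (minor)

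*Combined protocol and SAP*

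**What the plan says.** Section 4.3.1.1 makes related non-haematological toxicity of Grade 3 or higher dose limiting, subject to a list of clarifications. One bullet covers Grade 3 metabolic toxicities and gives glucose, potassium, magnesium, phosphate and sodium disturbances as examples. If not corrected to Grade 2 or lower within 24 hours, these "will be considered dose limiting, unless patient had metabolic abnormalities at baseline". The same bullet adds: "Grade 4 metabolic toxicities that are symptomatic will be considered dose-limiting regardless of duration or ability to correct". The next bullet says that other Grade 3 laboratory abnormalities count only if they do not resolve within two weeks.

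The count feeds two rules. Section 2.1.1: "The MTD will be defined as the highest dose that causes dose limiting toxicities (DLTs) in <2 of 6 patients". Section 4.3, after expansion to six patients: "If 1 of 6 total experiences a DLT, then escalation will proceed to the next level".

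Inclusion criterion 3.1.9 admits patients with potassium, sodium or corrected calcium up to Grade 1 and sets no limit on glucose. The chemistry panel (section 5.0, footnote 6) contains glucose, sodium, potassium and calcium, but not magnesium or phosphate. The summary of changes gives the reason for the exemption, added in Amendment 2, as flexibility for patients with metabolic abnormalities at baseline.

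**The concern.** A baseline exemption is reasonable when the patient entered with the disturbance that later reaches Grade 3, because attribution to nivolumab is then doubtful. This clause goes further. It asks only whether the patient had some metabolic abnormality at entry, so an abnormality in one analyte can excuse a new event in another.

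Sodium is a relevant example. Section 8.2.10 lists hyponatraemia at 25-38% with nivolumab alone, with no grade given. A patient who enters with raised glucose, which eligibility allows, and then develops a related Grade 3 hyponatraemia that is uncorrected at 24 hours would be counted as DLT-free.

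What is at stake is the accuracy of the Phase I count. One reclassified event can turn two DLTs in six into one. The clause applies at both dose levels, so it can ease escalation from 80 mg and acceptance of 240 mg, and it cannot work in the other direction. Section 1.3.1 justifies escalation by the lack of data on nivolumab with Y-90, which is a reason to want an exact DLT definition.

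**Working it through.** **Does another provision restore the event?** Take a related Grade 3 hyponatraemia, uncorrected at 24 hours, in a patient whose only baseline abnormality was glucose.

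- *Grade 4 sentence, 4.3.1.1.* It covers symptomatic Grade 4 events only, so it does not reach this case.
- *Bullet on other Grade 3 laboratory abnormalities, 4.3.1.1.* It follows the metabolic bullet and is limited to other abnormalities, so it does not clearly recapture an exempted metabolic one. Even if it did, the event would have to last two weeks.
- *Delay as a DLT, 4.3.1.* "Delay in starting nivolumab therapy more than 2 weeks due to toxicity regardless of attribution or grade, is considered a DLT". This concerns starting nivolumab, not a later dose.
- *Dosing delays, 4.4.1.* Doses are held for "Any Grade 3 drug-related laboratory abnormality, with the following exceptions for lymphopenia, leukopenia, AST, ALT, or total bilirubin". Sodium is not among the exceptions, so the dose is held, but the DLT count does not change.
- *Recording of a diagnosis, 7.2.1.* Where one has been made, "that diagnosis or syndrome should be recorded as the AE whenever possible". An event recorded that way may count under the lead sentence of 4.3.1.1. This is a partial route back, available only if a diagnosis is made.
- *DSMC review, 4.3.* The committee confirms DLTs under this same definition.

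On the literal text the event is therefore not counted.

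**How large is the effect?** The plan states no figure to reproduce and gives none of the rates needed. All four inputs below are assumptions:

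- m = 1-5%: chance that a patient has a related, persistent Grade 3 metabolic event in the 28-day window
- q = 0.5: share of such patients exempt as written
- k = 25-75%: share of those exempt patients who would stay exempt under a narrower rule, so that q becomes 0.5k
- o = 10-20%: rate of all other DLTs

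Formulas, taking the two sources of DLT as independent:

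- Counted DLT rate: p = 1 − (1 − m(1 − q))(1 − o)
- At most one DLT in six: (1 − p)^6 + 6p(1 − p)^5
- Escalation from level 1 (0 of 3, or 1 of 3 then 0 of 3): (1 − p)^3 + 3p(1 − p)^2(1 − p)^3

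Worked case, m = 0.05, k = 0.25, o = 0.15:

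- As written: p = 1 − 0.975 × 0.85 = 0.1713
- Narrower rule: q = 0.125, so m(1 − q) = 0.04375 and p = 1 − 0.95625 × 0.85 = 0.1872

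Each probability cell shows narrower rule → as written:

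| m | k | o | p | At most 1 DLT in 6 | Gain (points) | Escalate from level 1 | Gain (points) |
|---|---|---|---|---|---|---|---|
| 0.01 | 0.75 | 0.10 | 0.1056 → 0.1045 | 0.874 → 0.877 | 0.2 | 0.897 → 0.899 | 0.2 |
| 0.02 | 0.50 | 0.10 | 0.1135 → 0.1090 | 0.858 → 0.868 | 0.9 | 0.883 → 0.891 | 0.8 |
| 0.05 | 0.25 | 0.10 | 0.1394 → 0.1225 | 0.801 → 0.839 | 3.8 | 0.835 → 0.867 | 3.2 |
| 0.05 | 0.25 | 0.15 | 0.1872 → 0.1713 | 0.687 → 0.726 | 3.9 | 0.736 → 0.770 | 3.4 |
| 0.05 | 0.25 | 0.20 | 0.2350 → 0.2200 | 0.570 → 0.606 | 3.6 | 0.632 → 0.665 | 3.3 |

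Gains are computed before rounding. The first row is the smallest effect in the assumed ranges. The largest, about 3.9 and 3.4 points, occur near a 15% other-DLT rate.

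A patient has a wrongly excused event with probability m × 0.5 × (1 − k), that is 0.00125 to 0.01875. The chance of at least one among six patients is 1 − (1 − 0.00125)^6 = 0.7% up to 1 − (1 − 0.01875)^6 = 10.7%.

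**The case against.** The strongest reply is that a clinician would read the clause as meaning the corresponding abnormality. Section 4.4.1 ties its baseline rule to named liver tests, and section 7.2.6 judges a pre-existing condition by whether that condition worsens. That may well be the intent, but 4.3.1.1 does not say it, and two readers could classify the same event differently. If it is the intent, the fix only records it.

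The second reply is that the path is narrow. The event must be related to nivolumab, metabolic, Grade 3, persistent at 24 hours and within 28 days, in a patient whose baseline abnormality lay elsewhere. This stands, and it is why the point is minor.

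The third is that every rate in the calculation is assumed. This also stands. A reader might take the 25-38% hyponatraemia figure as the event rate, but it carries no grade and comes from melanoma and lung cancer monotherapy, so it shows only that the example is relevant. A reader might also obtain a larger effect by treating every exempted event as wrongly lost. That would charge the clause for exemptions that a narrower rule would keep.

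Finally, the exemption was deliberate. The flexibility that Amendment 2 sought survives a same-disturbance limit.

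**Conclusion.** The clause is broader than its purpose requires. As written, a metabolic abnormality unrelated to the toxicity can cancel a DLT, nothing else in the plan clearly restores it, and the error can only favour the dose. Severity is minor. The gain is about 0.2 to 3.9 percentage points in the chance of at most one DLT in six, and about 0.2 to 3.4 in the chance of escalating from 80 mg. Both ranges rest wholly on the assumed rates, and the upper ends need the highest event rate together with the lowest retained share.

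A reader might infer that the MTD is unreliable or that patients are left unprotected. The documents support neither. Nothing shows that the clause was applied across analytes, symptomatic Grade 4 events always count, and dose holding under 4.4.1 does not depend on the exemption. The conclusion is limited to a possible wrong count for the Phase I primary endpoint.

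**What to change.** In 4.3.1.1, replace the baseline condition with: *unless the same analyte was abnormal in the same direction at baseline; an analyte with no baseline value is treated as normal*. The direction matters because, without it, high glucose at entry would still excuse a Grade 3 low glucose.

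The cost is one phrase. No new tests are needed, because the screening panel already gives baselines for glucose, sodium, potassium and calcium, and the sample size is unchanged. The downside is that a few more events may count as DLTs. These may include an occasional undetected pre-existing magnesium or phosphate abnormality found by unscheduled testing, since neither analyte is in the screening panel.

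If Phase I enrolment is already complete, check whether any Grade 3 metabolic event was exempted because of a different baseline abnormality, and report the result with the DLT count.
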